Probiotics also found to have an effect in inducing, maintaining and increasing the remission period in UC and this effect suggested to be also associated with the immunomodulator role of certain microorganisms (Tamaki *et al.* 2016). For example, *in vitro* studies, *Lactobacillus casei* strain Shirota found to have anti-inflammatory effect by inhibition of IL-6 and interferon c (IFN-c) synthesis in lipopolysaccharide (LPS)-stimulated murine chronic IBD cells (Matsumoto *et al.* 2005), and *Lactobacillus delbrueckii* had anti-inflammatory effect by inhibition of NF- κ B pathway in large intestinal lamina propria mononuclear cells (Santos Rocha *et al.* 2012). *In vivo*, *Lactobacillus delbrueckii* and *Lactobacillus fermentum* supplementation, in UC patients undergoing treatment with sulfasalazine (an anti-inflammatory medicine) showed a reduction in several pro-inflammatory parameters in the colon, such as IL-6 levels, tumor necrosis factor TNF- α and NF- κ B p65 expression, and leukocyte recruitment, in comparison with the placebo and medical treatment groups (Hegazy and El-Bedewy 2010). In another study where *Bifidobacterium breve* was administrated as a part of a symbiotic, the results showed a significant decrease in the inflammatory parameters and improvement in the clinical status evaluated by colonoscopy in patients with mild to moderate UC (Ishikawa *et al.* 2011). Moreover, administration of probiotic product Bifid Triple Viable, that contains *Lactobacillus acidophilus*, *B. bifidum* and *Streptococcus*, for 2 months, lead to reduce the expression of IL-1b and increased the expression of IL-10 and immunoglobulin A (IgA) in the colon of UC patients (Li *et al.* 2012).

Materials and Methods:

Study Design

An interventional double-blind randomized controlled trial (RCT) design will be used in this study. A placebo group will be included parallel with the treatment group in this study. Forty IBD patients with mild to moderately active UC aged 18-65 will be recruited conveniently from the gastroenterology section, the IBD clinic at the Jordan University Hospital and Al-Bashir Hospital, Amman, Jordan. Patients who meet the inclusion criteria and agree to participate will be centrally

randomized to probiotic supplementation group or placebo group using computer-generated

random numbers, stratified by age and gender. The duration of intervention will be 6 weeks. **The**

study scheme:

The Interventions

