The probiotics and placebo treatments will be given at weekly basis in double blind manner for the six weeks. The patients in the probiotics group will receive 3 oral viable capsules of Jamieson Probiotic 10 Billion product, each of which contain ($1*10^{10}$ CFU/g) of *lactobacillus* (*Lactobacillus rhamnosus* HA-111, *Lactobacillus acidophilus* HA-122, *Lactobacillus salivarius* HA-118, *Lactobacillus paracasei* HA-196) and *bifidobacterium* (*Bifidobacterium breve* HA-129, *Bifidobacterium bifidum* HA-132 HA, *Bifidobacterium longum* HA-135) species three times a day. Similarly, the placebo group will receive 3 placebo capsules containing maltodextrin three times a day.

Human Participants:

Inclusion and Exclusion Criteria:

Inclusion criteria will be patients with age between 18 -70 years and diagnosed with UC established by colonoscopy and histology, and suffering from mild to moderate UC as defined by Modified Mayo Disease Activity Index (MMDAI, table 1) (score 3–9), the diagnoses will be done by a physician (Ng *et al.*, 2010; Palumbo *et al.*, 2016; Tamaki *et al.* 2016). Patients will be excluded if they had age <18 years, >70 years, pregnancy, planned pregnancy, breastfeeding, evidence of severe disease (MMDAI >10), concurrent enteric infection, use of antibiotics within the past 2 weeks, change in dose of oral 5-aminosalicylic acid (5-ASA) within the past 4 weeks, and use of rectal 5-ASA or steroids within 7 days before entry into the study, or the use of probiotic preparations during study, received any investigational medicines within 3 months, and if they have significant hepatic, renal, endocrine, respiratory, neurological, or cardiovascular diseases were also excluded (Ng *et al.*, 2010; Bengtsson *et al.*, 2016; Tamaki *et al.* 2016; Palumbo *et al.*, 2016).

Table 1. Modified Mayo Disease Activity Index.

Grade	Bowel frequency	Rectal bleeding	Physician's global assessment	Endoscopy/sigmoidoscopy finding
0	Normal number of stools per day for this patient	No blood seen	Normal	Normal or inactive disease
1	1 or 2 more stools than normal	Streaks of blood with stool less than half the time	Mild disease	Mild disease (erythema, decreased vascular pattern)
2	3 or 4 more stools than normal	Obvious blood with stool most of the time	Moderate disease	Moderate disease (marked erythema, absent vascular pattern, friability, erosions)
3	5 or more stools than normal	Blood alone passed	Severe disease	Severe disease (spontaneous bleeding, ulceration)

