Three parts package was used for collecting data that met the purpose of this study, including a personal questionnaire, physical activity questionnaire, and a short inflammatory bowel disease questionnaire (SIBDQ). A face-to-face interview technique was used as a method for data collection. Data on age, body weight, educational level, previous and current health problems, family history of IBD, and probiotic use were collected. The physical activity level was measured using a 7-day Physical Activity Recall (PAR) which was originally developed by Sallis *et al.*, 1985 (Sallis *et al.*, 1985). For assessing the quality of life, a disease-specific, validated, and reliable Arabic version of the SIBDQ obtained from the McMaster short IBD questionnaire at McMaster University was used (Mahalli and Alharthi, 2017). The SIBDQ contains ten questions covering the four HRQOL domains (systemic, social, bowel, and emotional) which were calculated and scored. The response to each question of the ten was graded on a 7-point Likert scale ranging from 1 (worst aspect) to 7 (best aspect). The total SIBDQ scores range from 10 to 70, with higher scores indicating better HRQOL (Mahalli and Alharthi, 2017). The summation of the responses to Q4, Q6, and Q9 was used for the bowel domain, the sum of the responses to Q2 and Q3 was for the social domain, the sum of the responses to Q1 and Q7 was for the systemic domain, and the sum of the responses to Q5, Q8, and Q10 was for the emotional domain. The total score of SIBDQ was composed of the sum of the responses to all ten questions (Guyatt *et al.*, 1989; Mahalli and Alharthi, 2017).

Statistical Analysis:

Statistical analysis will be done using IBM SPSS Statistics 20.0 software (version 20.0, IBM, Inc., Chicago, IL, USA). Mean \pm standard deviation (SD) will be used to express the continuous data and percentage to express the categorical data. The categorical variables will be compared using the Chi square and the continuous variables will be compared using the one-way ANOVA. A

paired *t*-test will be used to assess within-group changes in outcomes from baseline to end of intervention. For all data, *P*< 0.05 will be considered statistically significant.

References

Abraham, B. P., and Quigley, E. M. (2017), Probiotics in inflammatory bowel disease. **Gastroenterology Clinics**, 46(4), 769-782.

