Effect Of Probiotic Supplementation on The Immune System in Patients with Ulcerative Colitis in Amman, Jordan

By

[name]

Supervisor

[name] [name]

Co-Supervisor

[name] [name]

Funded by the University of Jordan

22 November 2023

NCT04223479

Statistical Analysis

Statistical analyses were performed using Statistical Package for Social Science (IBM® SPSS® Statistics; Version 21.0, version for Windows, 2019, USA). Mean and standard deviation (SD) were calculated for the continuous variables. Frequencies and percentages were used to describe categorical variables. The frequency of participants in terms of categorical variables was compared using the X² test. To check the normal distribution of continuous variables, the Shapiro-Wilk test was applied. Independent samples T-test was used to detect differences between placebo and probiotics groups in terms of continuous variables. A paired t-test was used to assess withingroup changes in biochemical parameters (IgG, IgM, IgA, IL-1, IL-6, IL10, TNF-α, and CRP) from baseline to the end of the study. A p-value < 0.05 was considered statistically significant. All outcomes were calculated by intention-to-treat (ITT) and perprotocol (PP) analyses. For ITT analysis, all randomized patients who took at least one tablet of study medication were included. For PP analysis all protocol violators (patients' dropout or loss of follow-up) were excluded.

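### With unadjusted t-tests and no stated missing-data method, the week-6 ITT and PP analyses may use the same completers; a baseline-adjusted comparison with numbers analysed should be the main result

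*SAP*

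**What the plan says.** The SAP (Statistical Analysis) states: "All outcomes were calculated by intention-to-treat (ITT) and perprotocol (PP) analyses". The ITT set is defined thus: "For ITT analysis, all randomized patients who took at least one tablet of study medication were included". The PP set removes protocol violators, and the only gloss on that term is the bracket ending "dropout or loss of follow-up) were excluded".

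For the between-arm comparison: "Independent samples T-test was used to detect differences between placebo and probiotics groups in terms of continuous variables". The SAP does not say whether the variable compared is the week-6 value or the change from baseline. Within arms, the SAP uses a paired t-test on the biochemical parameters. The protocol (Statistical Analysis) likewise plans a paired test that "will be used to assess within-group changes in outcomes from baseline to end of intervention". For continuous variables the protocol names one-way ANOVA, which with two arms is the equal-variance t-test.

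Neither document names imputation, carry-forward, a mixed model or any other way of treating a missing end value. Neither says whether patients who stopped early were still sampled at week 6. The protocol's exclusion list includes "or the use of probiotic preparations during study", but the SAP does not say whether a patient who did this leaves the PP set.

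**The concern.** Reporting ITT and PP side by side is useful when the two analyses use different patients. Here the one PP violation that the SAP names is the event that usually removes a patient's end value. If such patients have no week-6 value and none was supplied, the t-test drops them under ITT as well, and the two columns of results come from the same people.

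Two things would then be at stake. Agreement between the columns would carry no information about sensitivity to dropout. The ITT label would also not tell the reader that some randomised, treated patients are absent from the test. If values were instead filled in, the ITT result would depend on a rule that the SAP does not disclose.

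Separately, an unadjusted t-test in a trial of this size leaves chance baseline differences between arms uncorrected and does not use the baseline values that the paired tests already require.

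**Working it through.** The plan gives no figure on this point to reproduce: 40 patients are planned, with no derivation and no dropout allowance.

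**Inputs**
- Sample size, from the protocol (Study Design): "Forty IBD patients with mild to moderately active UC".
- Two arms, from the same section: "randomized to probiotic supplementation group or placebo group using computer-generated". The ratio is not stated; 20 per arm is assumed.
- Follow-up is 6 weeks (protocol, Study Design). The significance level is 0.05 (SAP), taken as two-sided.
- Baseline to week-6 correlation ρ is not given; 0.3 to 0.7 is assumed, with equal SD σ at both times.

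**Step 1: which patients each test uses.** Let D be the patients who dropped out or were lost, and W the patients with a week-6 value.
- ITT t-test uses ITT ∩ W.
- PP t-test uses (ITT minus D) ∩ W, if the bracket is the whole definition.
- If nobody in D is in W, then (ITT minus D) ∩ W = ITT ∩ W, and the two tests are the same test. The paired t-test behaves in the same way.

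The sets separate if some of D are in W (measured or filled in). They also separate if PP excludes completers for some other violation.

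**Step 2: check by simulation.** There were 1,000 trials per setting, with 20 per arm, an assumed effect of 0.5 SD, ρ about 0.5, and 2, 4, 8 or 12 of 40 dropping out at random. With no week-6 value for dropouts and no filling in, the ITT and PP p-values were identical in 100% of trials at every dropout number, for the between-arm test and both paired tests. With dropouts' values measured, or filled in by carrying baseline forward, the between-arm p-values were identical in 0% of trials.

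**Step 3: what baseline adjustment gains.** With n per arm, the variance of the estimated arm difference is:
- week-6 t-test: 2σ²/n
- change t-test: 2 × 2σ²(1 − ρ)/n
- ANCOVA: 2σ²(1 − ρ²)/n

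So ANCOVA has 1 − ρ² of the variance of the week-6 t-test. Against the change t-test it has (1 − ρ²)/[2(1 − ρ)] = (1 + ρ)/2.

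| ρ | vs week-6 t-test | vs change t-test |
|---|---|---|
| 0.3 | 1 − 0.09 = 0.91 | 1.3/2 = 0.65 |
| 0.5 | 1 − 0.25 = 0.75 | 1.5/2 = 0.75 |
| 0.7 | 1 − 0.49 = 0.51 | 1.7/2 = 0.85 |

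These ratios ignore the cost of estimating the slope. For normal baselines and 20 per arm, that cost multiplies the ANCOVA variance by (2n − 3)/(2n − 4) = 37/36 = 1.03. The ratios then become 0.94, 0.77 and 0.52 against the week-6 t-test, and 0.67, 0.77 and 0.87 against the change t-test. ANCOVA remains ahead of both throughout the assumed range.

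**The case against.** The coincidence is conditional and close to a tautology: a patient without a week-6 value cannot enter a week-6 test. The SAP's wording can also be read against it. It says that all outcomes were calculated by ITT and that every randomised patient who took a tablet was included. Taken literally, dropouts' values must have been measured or filled in, so the sets differ and only a reporting gap remains. The bracket may merely illustrate what counts as a violation, or users of other probiotics may have been withdrawn and so left PP as dropouts. ANCOVA, finally, is about precision and baseline imbalance; it brings no dropout back.

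Most of this stands. It is why the point is stated with both exceptions and why ANCOVA is not offered as a cure for dropout. It does not remove the point, because the text does not settle which reading applies, and under each reading something the reader needs is missing.

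A reader might go further and infer that significant results would be lost if dropouts were counted. The documents do not support that: they give no dropout rate and no results, and the direction depends on the method chosen. For example, assume a 1 SD effect and 10% lost per arm, and compare the SAP's week-6 t-test on completers with an ANCOVA after imputing from the placebo arm. The average t falls from about 3.05 to 2.75 at ρ = 0.3 but rises from about 3.05 to 3.58 at ρ = 0.7.

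**Conclusion.** The point holds in conditional form. If the bracket is the full PP definition and dropouts had no week-6 value measured or filled in, the week-6 ITT and PP analyses are one analysis reported twice. With no dropout the effect is nil. With dropout, agreement between them is uninformative about it. As an illustration only, a loss of 10% to 20% would leave 40 × 0.90 = 36 down to 40 × 0.80 = 32 patients in both analyses.

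It should not be inferred that the trial's ITT and PP results did coincide, because the documents report neither the dropouts nor how missing values were handled. Nor should it be inferred that the sponsor presents their agreement as evidence of robustness; neither document says so. It also cannot be said whether non-adherent completers or users of other probiotics stay in PP.

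The firmest part is the choice of test. Adjusting for a baseline already collected lowers the variance to 0.91 to 0.51 of that of the week-6 t-test, or 0.65 to 0.85 of that of the change t-test. This assumes correlations of 0.3 to 0.7, equal SDs and equal arms, before the small slope-estimation cost shown above.

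**What to change.** 1. Make the main between-arm comparison for each continuous outcome an ANCOVA of the week-6 value on arm and baseline value.
2. Report the number analysed per arm and per outcome. Label the result as all available week-6 data, not full ITT, unless dropouts' values were measured or were filled in by a rule that the SAP states.
3. State whether dropouts were sampled at week 6 or had values supplied, and how. State whether the bracket is the complete PP definition or a list of examples.
4. An imputation analysis covering dropouts is optional. It is a trade-off that rests on its own assumption. If done, its population must be named, since all randomised patients and all treated patients are different sets and the SAP's ITT is the latter.

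The cost is SAP wording and one ANCOVA per outcome on data already collected, with no new visit or sample. The SAP is written in the past tense, so if the analysis is finished the ANCOVA must be labelled post hoc. The remaining downside is one more set of results to report.
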